2.4.5 Analyses of safety data

The summary of safety results will be presented by treatment group.

General common rules

All safety analyses will be performed on the safety population as defined in [Section 2.3.2](#), unless otherwise specified, using the following common rules:

- Safety data in patients who do not belong to the safety population (eg, exposed but not randomized) will be listed separately.
- The baseline value is defined as the last available value before the first administration of the IMP.
- The potentially clinically significant abnormality (PCSA) values are defined as abnormal values considered medically important by the Sponsor according to predefined criteria/thresholds based on literature review and defined by the Sponsor for clinical laboratory tests, vital signs, and ECG (PCSA version dated May 2014 [[Appendix A](#)]).

- PCSA criteria will determine which patients had at least 1 PCSA during the TEAE period, taking into account all evaluations performed during the TEAE period, including unscheduled or repeated evaluations. The number of all such patients will be the numerator for the treatment-emergent PCSA percentage.
- The treatment-emergent PCSA denominator by group for a given parameter will be based on the number of patients assessed for that given parameter in the TEAE period by treatment group on the safety population.
- For quantitative safety parameters based on central laboratory/reading measurements, descriptive statistics will be used to summarize results and change from baseline values by visit (baseline and post-baseline time points) and treatment group. Summaries will include the last and the worst on-treatment value. Only data sampled before or on the day of the last IMP administration will be included in the analysis. The worst on-treatment value is defined as the nadir and/or the peak post-baseline before or on the day of the last IMP administration according to the direction (minimum or maximum) of the abnormality as defined in the PCSA list.
- All measurements (scheduled or unscheduled) will be assigned to time points according to analysis windows as defined in [Section 2.5.4](#).
- The analysis of the safety variables will be essentially descriptive and no systematic testing is planned. Relative risks versus placebo and their 95% confidence intervals may be provided, if relevant.

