c Study treatment is to be administered once a week, either at the site or at home by a qualified healthcare professional – Last dose will be given at Week 23

d Complete physical examinations will include skin, nasal cavities, eyes, ears, respiratory, cardiovascular, gastrointestinal, neurological, lymphatic, and musculoskeletal systems. For the dermatological examination the Investigator should evaluate for SSc related skin changes and some specific findings that may indicate vasculitis including, but not limited to: purpura, papules or non-blanching rashes. Nail beds (periungual areas) should be examined for “splinter lesions” and digital tuft for tuft purpura or ischemia. Gynecological and urogenital examinations will not be done in this study unless for cause

e Vital signs, including blood pressure (mmHg), heart rate (beats per minute) and body weight (kg) will be measured at screening, baseline and every subsequent visit. Height (cm) will be measured at screening (Visit 1) only. BMI will be calculated automatically at all visits

- f* All abnormal ECG interpretation will be reviewed and confirmed by a local cardiologist.
- g* Previous echocardiogram may be used if obtained within 6 months of V1 (screening visit).
- h* Hematology: Hemoglobin, hematocrit, red blood cell count, erythrocyte sedimentation rate (ESR), white blood cell count with differential and platelet count. Biochemistry: Fasting glucose, blood urea nitrogen, creatinine, sodium, potassium, chloride, bicarbonate, calcium, phosphorous, total protein, albumin, total bilirubin, alkaline phosphatase, ALT, AST, CPK, hs CRP. Urinalysis (dipstick) to include: specific gravity, pH, glucose, ketones, blood, protein, nitrate, leukocyte esterase, urobilinogen and bilirubin. If any parameter on the dipstick is abnormal, a urine sample should be sent to the central laboratory for testing. If positive for protein and/or red blood cells, microscopic analysis will be performed by the central laboratory
- i* Serology testing includes HIV-1/HIV-2 antibody, hepatitis B surface antigen, hepatitis B surface antibody, hepatitis B core antibody, hepatitis B DNA (reflex to a positive hepatitis B core antibody), hepatitis C antibody and hepatitis C RNA (reflex to a positive hepatitis C antibody)
- j* [REDACTED]

- k* Tuberculosis screen: history and QuantiFERON-TB Gold test. If the result of the initial QuantiFERON-TB Gold test is indeterminate, the test should be repeated one time

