8.1.4 Route and method of administration

The route and method of administration are SC in the abdomen. SC injection sites should be alternated between the 4 quadrants of the abdomen (avoiding navel and waist areas) so that the same site is not injected for two consecutive weeks. The exact site of each injection will be documented on the source document. It is recommended that the injection occur at a site free of SSc involvement, if possible.

The IMP is administered every 7 days ± 2 days from initial IMP administration. This window is permitted per protocol to accommodate various circumstances (eg, pending laboratory results, management of AE, visit scheduling difficulty). The IMP administration should be performed by other site personnel, blinded from the person in charge of the preparation of the solutions and syringes.

If IMP administration is missed or temporarily discontinued, the initial schedule of injections may be resumed upon the investigator's medical judgment and discretion while the missed dose(s) will not be administered. This does not apply to permanent treatment discontinuation.

On days when the patient has a study visit, the IMP will be administered by the Investigator or delegate after clinic procedures and blood collection.

For doses not administered at the study site, the IMP will be administered by qualified site personnel and /or healthcare professionals (eg, visiting nurse service).

Patients should be monitored by site personnel/visiting nurse for at least 30 minutes or up to 2 hours as per country specific requirements after each administration for potential signs and symptoms that may suggest a hypersensitivity reaction.

For doses not given at the study site, a booklet will be provided to the patient to record information related to the injections; this booklet will be completed by the visiting nurse after each injection and will be kept as source data in the patient's study file. Patients will be instructed to bring the booklet back at the subsequent site visit for Investigator's review.

Between the protocol-scheduled on-site visits, interim visits to the site may be required for IMP dispensing. As an alternative to these visits, the IMP may be supplied from the site to the patient via a Sponsor-approved courier company where allowed by local regulations and approved by the patient.

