- Provide treatment kits to be administered at Weeks 9, 10 and 11
- Schedule an appointment for the next visit, Visit 6 (Week 12)

10.1.7 Visit 6: on treatment/Week 12

- Questionnaires/forms to be completed:
 - SHAQ (by patient)
 - UCLA SCTC GIT 2.0 (by patient)
 - EQ-5D-5L (by patient)
 - Patient Global Assessment (by patient)
 - Physician Global Assessment (by Investigator)
- Record all concomitant medication use
- Inquire about AEs/SAEs
- Inquire Resource Utilization (Refer to [Section 9.3.2](#))
- Assess for Step 1 of CRISS (cardiopulmonary and/or renal involvement)
- Review patient booklet to assess local tolerability at the injection site and treatment compliance
- Record vital signs including BP, heart rate and weight
- Perform a complete physical examination (Refer to [Section 9.2.2.1](#)), including:
 - Perform the mRSS
 - Perform a TJC28
 - Perform a digital ulcer count
- Perform 12-lead ECG
- Blood and Urine Testing
 - Obtain blood samples for complete clinical laboratory determinations including hematology and biochemistry profile
 - Obtain urine for urinalysis (dipstick)
 - For women of childbearing potential:
 - Perform urine pregnancy test. The patients should be instructed to do the urine pregnancy test at home on a monthly basis during the intervals in between on-treatment study visits for the duration of the study. In case of a positive pregnancy test, the patient should be advised to contact immediately the investigator.
 - Dispense urine pregnancy test kits for monthly urine pregnancy tests (sufficient monthly supplies to last until the next scheduled on-site visit).
 - Obtain blood sample for serum SAR156597 level (PK) and for anti-SAR156597 antibody (ADA)
 - Obtain blood sample for ANCA and complements (C3, C4 and CH50)
 - Obtain blood samples for protein biomarkers analysis

- Obtain blood samples for archiving for future protein assays and mRNA analysis (only for those patients who have signed a separate Future Use of Samples informed consent form)
- Perform PFTs: observed and % predicted FVC, and observed and % predicted DLco (corrected for hemoglobin)
- Call IVRS to dispense a 6 week treatment kit allocation (Weeks 12, 13, 14, 15, 16, and 17)
 - Reminder: Make an additional IVRS call (as per study flow chart [[Section 1.2](#)]) at Week 18 to dispense an additional 6 week supply of IMP which will be required for Weeks 18, 19, 20, 21, 22 and 23.
- Administer IMP for Week 12

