2.1.5 Safety endpoints

The safety analysis will be based on the reported adverse events and other safety information, such as clinical laboratory data, vital signs, ECG.

Observation period

The observation period will be divided into 4 epochs:

- The **pre-treatment** epoch is defined as the time from the signed informed consent date up to the first administration of IMP.
- The **treatment** epoch is defined as the time from the first administration of the IMP to the last administration of the IMP + 7 days.
- The **residual treatment** epoch is defined as the time from the last administration of the IMP + 8 days to the last administration of the IMP + 84 days.

The treatment-emergent adverse event (TEAE) period will include both **treatment** and **residual treatment** epochs.

- The **post-treatment** epoch is defined as the period of time starting the day after the end of the TEAE period up to the end of the study (defined as last protocol-planned visit or last study assessment).

The on-study observation period is defined as the time from the first administration of IMP until the end of the study (defined as last protocol planned visit or last study assessment).

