2.4.4.1.3 On-treatment analysis

A secondary estimand will be the difference in mean change from baseline to 24 weeks in mRSS estimated during the on-treatment period (from the first administration of the IMP to the last administration of the IMP + 7 days). This estimand corresponds to a “while on treatment strategy”. This estimand will be considered for describing the effect of treatment as long as patients adhere to their randomized treatment.

As a secondary analysis, the change in mRSS from baseline to Week 24 will also be analyzed in the randomized and treated population using the same MMRM model as described above, including only post-baseline data measured during the on-treatment period (from the first administration of the IMP to the last administration of the IMP + 7 days), analyzed according to the treatment group allocated by randomization.

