2.4.5.3 Analyses of laboratory variables

The summary statistics (including number, mean, median, standard deviation, minimum and maximum) of all laboratory variables (central laboratory values and changes from baseline) will be calculated for each visit (baseline and post-baseline time points) and presented by treatment group. This section will be organized by biological function as specified in [Section 2.1.5.3](#).

For parameters creatinine, glucose, neutrophils, monocytes, basophils, eosinophils and bicarbonate, the last on-treatment and worst on-treatment value will also be provided.

The incidence of PCSAs (list provided in [Appendix A](#)) at any time during the TEAE period will be summarized by biological function and treatment group whatever the baseline level and/or according to the following baseline status categories:

- Normal/missing.
- Abnormal according to PCSA criterion or criteria.

For parameters for which no PCSA criteria are defined, similar table(s) using the normal range will be provided.

Listing will be provided with flags indicating the out of range values as well as PCSA values.

Drug-induced liver injury

The liver function tests, namely AST, ALT, alkaline phosphatase, and total bilirubin, are used to assess possible drug-induced liver toxicity. The proportion of patients with PCSA values at any post-baseline visit by baseline status will be displayed by treatment group for each parameter.

A graph of distribution of peak values of ALT versus peak values of total bilirubin will also be presented. Note that the ALT and total bilirubin values are presented on a logarithmic scale. The graph will be divided into 4 quadrants with a vertical line corresponding to $3 \times \text{ULN}$ for ALT and a horizontal line corresponding to $2 \times \text{ULN}$ for total bilirubin.

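### The last and worst on-treatment laboratory values stop at the day of the last dose (Week 23), so they leave out the Week 24 sample of in-window completers and, without unscheduled samples, end at Week 12

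*SAP*

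**What the plan says.** SAP 2.4.5, in its rule for quantitative central-laboratory parameters, states: "Only data sampled before or on the day of the last IMP administration will be included in the analysis". The next sentence builds the same limit into the worst on-treatment value, defined as the "nadir and/or the peak post-baseline before or on the day of the last IMP administration". Protocol 11.4.3.2 sets the same cut-off for laboratory data, and Protocol 11.4.3.4 sets it for vital signs.

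SAP 2.4.5.3 names the parameters concerned: "For parameters creatinine, glucose, neutrophils, monocytes, basophils, eosinophils and bicarbonate, the last on-treatment and worst on-treatment value will also be provided". SAP 2.4.5.4 plans last and worst values for heart rate and blood pressure without stating a cut-off.

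On timing, footnote c of the Protocol 1.2 flow chart says "Last dose will be given at Week 23". Protocol 10.1.7 describes the final supply as "required for Weeks 18, 19, 20, 21, 22 and 23". Protocol 8.1.4 fixes the window: "The IMP is administered every 7 days ± 2 days from initial IMP administration".

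Elsewhere the SAP draws the line differently. In SAP 2.1.5 the treatment "epoch is defined as the time from the first administration of the IMP to the last administration of the IMP + 7 days". SAP 2.4.4.1.3 uses, for the skin score, the "on-treatment period (from the first administration of the IMP to the last administration of the IMP + 7 days" definition. SAP 2.1.5.2 counts a death as on-treatment throughout the TEAE period, which runs to last dose + 84 days.

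**The concern.** A reader will take a last or worst on-treatment laboratory value in a 24-week treatment trial to cover the treatment period, including the visit that closes it. Under the SAP 2.4.5 cut-off it cannot, because the closing laboratory sample is scheduled a week after the final injection and the sample before that is at Week 12. Nothing in the table label would show this.

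The label is also used in three senses within one SAP: last dose + 0 days for laboratory values, + 7 days for the skin score and + 84 days for deaths. At nominal days, the same V7 visit is on-treatment for efficacy and off-treatment for laboratory safety.

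Safety is a secondary objective. PCSA tables count threshold crossings, whereas the last and worst summaries show the size of change, so a truncated version loses information of a different kind. The definition may also reach the liver normalization table in SAP 2.4.5.3, where one category covers patients with no later assessment than their worst on-treatment value.

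**Working it through.** **Inputs**
- Cut-off: last-dose day + 0 (SAP 2.4.5).
- Last dose: Week 23 (synopsis; Protocol 1.2 footnote c; Protocol 10.1.7). SAP 2.1.6 places Week 35 at 12 weeks after the last injection, and 35 − 12 = 23. The V7 procedures in Protocol 10.1.8 list no injection.
- Dosing window: ±2 days, counted from the first dose (Protocol 8.1.4). Visit window: ±2 days (Protocol 1.2 footnote a).
- Scheduled laboratory samples after baseline: Weeks 4, 8, 12, 24 and 35, plus early termination (SAP 2.1.5.3).
- Samples are taken before that day's injection (Protocol 9.2.2).

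**Reproducing the plan's own days.** Study day = 1 + 7 × week. Week 12: 1 + 84 = 85. Week 24: 1 + 168 = 169. Week 35: 1 + 245 = 246. All three match SAP Table 3. Week 23 is then 1 + 161 = 162.

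**Is V7 kept?**
- Last dose: 162 ± 2 = Day 160 to 164.
- V7: 169 ± 2 = Day 167 to 171.
- Gap: smallest 167 − 164 = 3 days, largest 171 − 160 = 11 days, nominal 7 days.
- Day pairs with a gap of 0 or less: 0 of 5 × 5 = 25.

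**What is left?**
- The last scheduled sample on or before the last dose is Week 12, Day 83 to 87. It comes 162 − 85 = 77 days before the last dose (160 − 87 = 73 to 164 − 83 = 81).
- Injections are planned at Weeks 0 to 23, which is 24. Those at Weeks 12 to 23, which is 12, follow the Week 12 sample.
- Without unscheduled samples, the worst value therefore comes from Weeks 4, 8 and 12, and the last value is Week 12.

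**Would a longer fixed limit solve it?**
- Last dose + 7 days keeps 15 of 25 pairs.
- Last dose + 11 days keeps 25 of 25, but only if the Week 23 dose is given. Protocol 8.1.4 does not make up missed doses. If only the final injection is missed, the last dose is at Week 22: Day 1 + 154 = 155, range 153 to 157. The gap to V7 is then 167 − 157 = 10 to 171 − 153 = 18 days, and + 11 days keeps 3 of 25 pairs.

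**What is not affected?**
- PCSA incidence runs to last dose + 84 days, so a gap of 3 to 11 days keeps V7 in 25 of 25 pairs.
- SAP Appendix A gives PCSA criteria for six of the seven parameters. Bicarbonate has none and gets a normal-range table under SAP 2.4.5.3.

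The counts are of possible day pairs, not expected proportions of patients.

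**The case against.** The strongest case on the other side is that the cut-off is a deliberate rule, written alike in protocol and SAP, and that its reach is small. SAP 2.4.5.3 plans by-visit statistics, including minimum and maximum, for every laboratory variable. If these follow Table 3, Week 24 values are reported in full. PCSA incidence and flagged listings keep Week 24, and no systematic safety testing is planned. All of that stands, and it limits the severity. It does not rescue the last and worst rows, whose label promises more than their content.

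A second objection is that V7 might be a dosing day. Protocol 9.3.1.1 and SAP 2.1.6 describe the V7/Week 24 drug-concentration sample as taken before a dose. If a dose were given that day, V7 would be kept. These passages conflict with the Week 23 statements, and SAP 2.1.6 also conflicts with itself, since it places Week 35 at 12 weeks after the last injection. They must be reconciled.

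A reader might infer that Week 24 laboratory data drop out of the safety analysis, or that abnormalities after Week 12 would go unseen. The documents do not support this, because PCSA tables and listings retain them. A reader might also infer that the by-visit Week 24 rows are emptied. The position of the sentence in SAP 2.4.5, and the wording of Protocol 11.4.3.2, leave that open. Table 3, however, defines safety windows for Weeks 24 and 35, so it cannot be asserted.

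**Conclusion.** The point holds for the last and worst on-treatment values of the seven laboratory parameters. The V7 sample is excluded for every completer within the windows (0 of 25 day pairs), and without unscheduled samples the values describe treatment only up to the Week 12 pre-dose sample. An effect on the liver normalization table is possible, not shown. Early stoppers are exposed too: a premature end-of-treatment sample drawn after the last-dose day is lost in the same way.

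Severity is minor to moderate, because only descriptive tables are touched. The result rests on three assumptions: a last dose at Week 23, dosing days counted from the first dose as in Protocol 8.1.4, and no unscheduled samples between Week 12 and the last dose. It does not rest on any reading of the by-visit summaries.

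**What to change.** In SAP 2.4.5:
1. Define last and worst on-treatment values as post-baseline values up to last dose + 7 days, which is the SAP's own treatment epoch. Add the end-of-treatment visit sample if it is later than that but within the TEAE period. That visit is V7 for patients who did not permanently discontinue and the premature end-of-treatment visit for those who did. Later off-drug visits of early stoppers do not count.
2. State that by-visit safety summaries follow the Table 3 windows with no last-dose cut-off.
3. Apply the same definition to the liver normalization table in SAP 2.4.5.3 and to the vital-sign values in SAP 2.4.5.4.
4. Record the change from Protocol 11.4.3.2 and 11.4.3.4 in SAP 1.6.
5. Reconcile the pre-dose V7 wording in Protocol 9.3.1.1 and SAP 2.1.6 with the Week 23 last dose.

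A visit-based addition is better than a longer fixed limit: + 7 days alone misses 10 of 25 in-window pairs, and + 11 days fails in 22 of 25 when just the final injection is missed.

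The cost is SAP wording and a changed selection condition in the programs, with no new data. The downside is that some samples more than 7 days after the last dose count as on-treatment. Showing days since last dose in the listing makes that visible.

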2.4.5.1 Analyses of adverse events

Generalities

The primary focus of adverse event reporting will be on TEAEs. Pre-treatment and post-treatment adverse events will be described separately.

If an adverse event date/time of onset (occurrence, worsening, or becoming serious) is incomplete, an imputation algorithm will be used to classify the adverse event as pre-treatment, treatment-emergent, or post-treatment. The algorithm for imputing date/time of onset will be conservative and will classify an adverse event as treatment emergent unless there is definitive information to determine it is pre-treatment or post-treatment. Details on classification of adverse events with missing or partial onset dates are provided in [Section 2.5.3](#).

Adverse event incidence tables will present by SOC, HLTG, HLT, and PT, sorted in alphabetical order for each treatment group, the number (n) and percentage (%) of patients experiencing an adverse event. Multiple occurrences of the same event in the same patient will be counted only once in the tables within a treatment phase. The denominator for computation of percentages is the safety population within each treatment group.

Sorting within tables ensures the same presentation for the set of all adverse events within the observation period (pre-treatment, treatment-emergent, and post-treatment). For that purpose, the table of all TEAEs presented by SOC and PT sorted by the internationally agreed SOC order and decreasing frequency of PTs within SOCs will define the presentation order for all other tables unless otherwise specified. Sorting will be based on results for the experimental treatment arm.

Analysis of all treatment-emergent adverse events

The following TEAE summaries will be generated for the safety population.

- Overview of TEAEs, summarizing number (%) of patients with any
 - TEAE,
 - Serious TEAE,
 - TEAE leading to death,
 - TEAE leading to permanent treatment discontinuation.
- All TEAEs by primary SOC, HLGT, HLT, and PT, showing number (%) of patients with at least 1 TEAE sorted by the SOC internationally agreed order. The other levels (HLGT, HLT, PT) will be presented in alphabetical order.
- All TEAEs by primary SOC and PT, showing the number (%) of patients with at least 1 TEAE, sorted by the internationally agreed SOC order and by decreasing incidence of PTs within each SOC. This sorting order will be applied to all other tables, unless otherwise specified.
- All TEAEs regardless of relationship and related to IMP by primary SOC, HLGT, HLT and PT, showing the number (%) of patients with at least 1 TEAE, sorted by the internationally agreed SOC order. The other levels (HLGT, HLT, PT) will be presented in alphabetical order.
- All TEAEs by maximal severity, presented by primary SOC and PT, showing the number (%) of patients with at least 1 TEAE by maximal severity (ie, mild, moderate, or severe), sorted by the sorting order defined above.

Analysis of all treatment emergent SAEs

- All treatment-emergent SAEs by primary SOC, HLGT, HLT, and PT, showing the number (%) of patients with at least 1 serious TEAE, sorted by the internationally agreed SOC order. The other levels (HLGT, HLT, PT) will be presented in alphabetical order.
- All treatment-emergent SAEs by primary SOC and PT, showing the number (%) of patients with at least 1 serious TEAE, sorted by the sorting order defined above.
- All treatment-emergent SAEs regardless of relationship and related to IMP, by primary SOC, HLGT, HLT, and PT, showing the number (%) of patients with at least 1 treatment-emergent SAE, sorted by the internationally agreed SOC order. The other levels (HLGT, HLT, PT) will be presented in alphabetical order.
- Listings will be provided for all SAEs by treatment arm during the TEAE period.

Analysis of all TEAEs leading to treatment discontinuation

- All TEAEs leading to treatment discontinuation, by primary SOC, HLT, HLT, and PT, showing the number (%) of patients sorted by the internationally agreed SOC order. The other levels (HLGT, HLT, PT) will be presented in alphabetical order.
- All TEAEs leading to treatment discontinuation, by primary SOC and PT, showing the number (%) of patients with at least 1 TEAE, sorted by the internationally agreed SOC order and by decreasing incidence of PTs within each SOC.
- Listing will be provided for all TEAE leading to permanent treatment discontinuation by treatment arm.

Analysis of treatment-emergent AESIs

All treatment-emergent AESIs, by AESI category and PT, showing the number (%) of patients by treatment group, sorted by decreasing incidence of PT within each AESI category. The AESIs categories and details of the MedDRA coding are provided in [Section 2.1.5.1](#).

- Listing of all Treatment emergent AESIs experienced per patient and by treatment arm: Patient ID, AESI category, PT, time to onset of event, date of first and last IMP administration, duration, intensity, corrective treatment, seriousness, relationship to SAR.

Analysis of pre-treatment and post-treatment adverse events

If any pre-treatment or post-treatment AE lead to death or any pre-treatment AE lead to treatment discontinuation, a listing will be provided.

